7.5 Study Duration

- 1) The duration of the whole PMOS is estimated to be about 4 years.

- Study start: September 2012
-

- Recruiting phase: September 2012 - December 2014
 - Data completion: January 2018
 - End of study: The date on which statistical analysis dataset for Clinical Study Report becomes available
 - Data analysis and final report: April 2018 – October 2018
- 2) For each individual patient, the PMOS starts with the enrollment at the beginning of the treatment with adalimumab.
- Observation period
 - 104 weeks (or discontinuation of this study)
 - Discontinuation of this study
 - Patients within 52 weeks into this study: When adalimumab treatment is discontinued.
 - Patients after 52 weeks into this study: When any biologics other than adalimumab is administered.

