9.3 Serious Adverse Event Collection Period

Serious adverse events will be reported to AbbVie GK from the time the physician obtains the patient's authorization to use and disclose information (or the patient's informed consent) until the end of the PMOS (week 104 or discontinuation of this study).

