13.1 Sample Size Calculation

The primary endpoint of this study is the proportion of subjects who achieve DAS28 (CRP) remission (DAS28 <2.6) after 52 weeks of adalimumab + high dose MTX. We calculated the target sample number for this survey on the basis of an expected remission

rate, i.e., the percentage of patients with a DAS28 score of <2.6, at week 52 during the treatment with adalimumab 40 mg and MTX at ≥ 12 mg/week.

Table 3 lists the percentages of patients with a DAS28 score of <2.6 at week 52 in a study conducted by Takeuchi et al.⁹⁾ in patients receiving adalimumab and MTX.

Table 3. Patients with a DAS 28 score of <2.6 at week 52 during the treatment with adalimumab and MTX

adalimumab + MTX dose (mg/week)	Percentage of patients with DAS28 <2.6 (Week 52)
8.5 ± 2.9	42.7% (61/143 patients)
≥ 12	61.7% (29/47 patients)

As Table 3 shows, 42.7% of patients receiving MTX at 8.5 ± 2.9 mg/week at the initiation of adalimumab treatment achieved a DAS 28 of <2.6 at week 52, and the corresponding percentage of patients receiving DAS at ≥ 12 mg/week at baseline was 61.7%. When 55% of patients receiving MTX at ≥ 12 mg/week at the initiation of adalimumab treatment are assumed to achieve a DAS 28 of <2.6 at week 52 (subtracting the standard error (7.10%) from the above mentioned percentage; $61.7 - 7.1 = 54.6\%$), the number of patients required to achieve a power ($1-\beta$) of 0.90 at an α level of 0.05 (two-tailed) would be 171 (one-sample test).

Since 32% of patients enrolled in the all-case survey of adalimumab in patients with rheumatoid arthritis dropped out during the 24-week survey period, we assumed that 50% of the participants in the survey would drop out during the 52-week survey period, and calculated that 342 patients should enroll in the survey. We thus set the target sample size at 350.

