4.3. Planned sample size

(1) Planned number of patients surveyed

350 patients

(2) Rationale for setting

The patient with Disease Activity Score 28 (hereafter, referred to as “DAS28”) below 2.6 at week 52 was estimated to be 55% (the expected observation was 55% and the estimated difference was 12.3% for the literature data 42.7%), and the number of patients required to detect at a 5% level of significance level (paired) and a 90% power was calculated to be 171 patients. As the number needed to treat to secure this number of patients, the dropout rate at week 52 in this survey was assumed to be 50% based on the dropout rate of approximately 32% at week 24 in the all-case surveillance with Humira, and the planned number of patients surveyed was calculated to be 350 patients.

5. Items to be evaluated in analysis and examining method

(1) Analysis items

1) Matters concerning patient composition

- 1) Number of patients with returned CRFs
- 2) Number of patients included in the safety analysis set
- 3) Number of patients included in the efficacy analysis set

- 2) Matters concerning safety
 - 1) List of incidences of ADRs/infections
 - 2) Factors considered to have an influence on safety
Incidence of ADRs by patient background factor, etc.
 - 3) AEs occurred during or after treatment
List of incidences of serious AEs, etc.
 - 3) Matters concerning efficacy
 - 1) DAS28 response, trend, percentage of remission, etc.
 - 2) CDAI response, trend, percentage of remission, etc.
 - 3) SDAI response, trend, percentage of remission, etc.
 - 4) Trends in HAQ, etc.
 - 5) Trends in EQ-5D, etc.
 - 6) Trends in mTSS/bone erosion score/joint space narrowing score and the percentage of patients without worsening of mTSS/bone erosion score/joint space narrowing score (change from the survey start < 0 and < 0.5), etc.
 - 7) Factors considered to have an influence on efficacy (list of efficacy by patient background factor, etc.)
- (2) Analysis methods
Appropriate methods including χ^2 test according to the scale and nature of the analysis data should be used.

6. Schedule of the analysis

Purpose of the analysis	Survey unit period and time frame for reexamination
The 11th Periodic Safety Report	December 31, 2012 - June 30, 2013
The 12th Periodic Safety Report	July 1, 2013 - December 31, 2013
The 13th Periodic Safety Report	January 1, 2014 - June 30, 2014
The 14th Periodic Safety Report	July 1, 2014 - December 31, 2014

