Treatment period (day) Completion date of treatment *Per record	
It should be between the start date of Humira treatment and the completion date of treatment per treatment record.
 
When the completion date of treatment in the information on the previous treatment within the same CRF and the start date of treatment in the information on the relevant treatment are the same date, the completion date of treatment in the information on the previous treatment should be - 1 day.
 
The records with the dose of 0 mg should be excluded from the analysis.

Dosing intervals (day) *Per record	Biweekly should be 14 days, once in three weeks should be 21 days, and once in four weeks should be 28 days, respectively.
Total number of doses	The total after calculating the number of doses per record by rounding up the first decimal place should be taken for treatment period (day)/dosing intervals (day).
Patients who discontinued Humira treatment	If the final fixed CRF is the first or second CRF, the patients should be handled as the patients with a description in the “treatment discontinuation” column in the final CRF. If the final fixed CRF is the third CRF, the patient should be handled as the patients with a description of the completion date of treatment in the final record of the “Humira treatment status” column in the final CRF.
Patients who are continuing Humira treatment	If the final fixed CRF is the first or second CRF, the patients should be handled as the patients without a description in the “treatment discontinuation” column in the final CRF. If the final fixed CRF is the third CRF, the patient should be handled as the patients with a description of “continuing” in the final record of the “Humira treatment status” column in the final CRF.
Date of treatment discontinuation	In patients who discontinued Humira treatment, the completion date of Humira treatment should be the date of discontinuation.
Low body weight	Patients with body weight of < 30 kg.
Date of survey discontinuation	It should be the date of survey discontinuation described in the third CRF. It should be the start date of treatment with other biological products, or the older date among the last follow-up date.
AE follow-up period	It should be between the date of initial Humira treatment and the date of initial Humira treatment + 755 days.

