Analysis object: Patients included in the safety analysis set

Purpose of analysis: To indicate the number of patients analyzed, number of patients who developed all events, number and percentage of ADRs, number and percentage of SOC and PT by seriousness regarding ADRs. The same PT of the same patient should be summarized collectively, and in that sense, the most serious event should be tabulated.

Note: The information on novelty should not be granted.

The next forms should be prepared in the same manner.

“Table 5.1.1 Frequency of AEs by seriousness”

Analysis object: Patients included in the safety analysis set

“Table 5.1.2 Frequency of ADRs by seriousness (excluded patients)”

Analysis object: Patients excluded from the safety analysis set

Note: Among the patients with fixed CRFs, the patients excluded from the safety analysis set should be tabulated.

“Table 5.1.3 Frequency of ADRs by seriousness (Hospital of the University of Occupational and Environmental Health, Japan)”

Analysis object: Patients included in the safety analysis set

Note: patients treated at the Hospital of the University of Occupational and Environmental Health, Japan should be tabulated.

“Table 5.1.4 Frequency of ADRs by seriousness (other than Hospital of the University of Occupational and Environmental Health, Japan)”

Analysis object: Patients included in the safety analysis set

Note: Patients excluded from those treated at the Hospital of the University of Occupational and Environmental Health, Japan should be tabulated.

“Table 5.2.1 Frequency of ADRs by time of onset”

Analysis object: Patients included in the safety analysis set

Purpose of analysis: To indicate the number of patients analyzed, number of patients who developed all ADRs, number and percentage of ADRs, number and percentage of SOC and PT by time of onset regarding ADRs.

Note: The information on novelty should not be granted.

Categories for time of onset of ADRs: “start of treatment to week 24,” “week 24 to week 52,” “week 52 to week 108,” and “after completion of treatment.”

“Table 5.2.2 Frequency of serious ADRs by time of onset”

Analysis object: Patients included in the safety analysis set

Purpose of analysis: To indicate the number of patients analyzed, number of patients who developed all events, number and percentage of ADRs, number and percentage of SOC and PT by time of onset regarding serious ADRs.

Note: The information on novelty should not be granted.

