“5.2.3 Summary of serious adverse drug reactions by each MTX Dose of Baseline”

Analysis object: Patients included in the safety analysis set

Purpose of analysis: To indicate the number of patients analyzed, number of patients who developed ADRs, number and percentage of ADRs, number and percentage of SOC and PT by category of MTX dose at the start of treatment regarding serious ADRs.

Note: Category of MTX dose at the start of treatment

“Baseline MTX 12<= $<$ 14.0,” “Baseline MTX 14.0<= $<$ 16.0,” “Baseline MTX 16.0<=”

This should be prepared only at the time of literature analysis.

“Table 5.2.4 Summary of serious adverse drug reactions by each MTX Dose of Baseline (Event/100 Patient Years)”

Analysis object: Patients included in the safety analysis set

Purpose of analysis: To indicate the number of patients analyzed, number of patients who developed ADRs, number and percentage of ADRs (unit: 100 persons/year), number and percentage of SOC and PT by category of MTX dose at the start of treatment regarding serious ADRs during Humira treatment.

Note: Category of MTX dose at the start of treatment

“Baseline MTX 12<= $<$ 14.0,” “Baseline MTX 14.0<= $<$ 16.0,” “Baseline MTX 16.0<=”

Percentage of patients who develop ADRs (person/year) = “number of serious ADRs / total follow-up period)

This should be prepared only at the time of literature analysis.

“Table 5.3.1 List of AEs occurred during treatment and after completion of treatment”

Analysis object: Patients included in the safety analysis set

Purpose of analysis: To indicate the number of overall ADRs, SOC and PT occurred by case status (overall, patients who are continuing Humira treatment, patients who discontinued Humira treatment) regarding AEs.

The patients who discontinued Humira treatment should be indicated by timing of treatment (during treatment, after treatment).

Note: The definitions of case status should be as follows.

- During treatment

Events that occurred between the date of initial Humira treatment and the date of final Humira treatment.

- After treatment

Events that occurred after the date of final Humira treatment.

“Table 5.3.2 List of serious AEs occurred during treatment and after completion of treatment”

Analysis object: Patients included in the safety analysis set

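### ADR percentages by onset window (SAP Tables 5.2.1 and 5.2.2) have no stated at-risk denominator; read naturally, they divide by the whole safety set although AE collection has ended for early stoppers

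*SAP*

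**What the plan says.** **Who is observed, and for how long.** Protocol 7.5 sets observation at 104 weeks or until the patient discontinues the study. Discontinuation has two definitions. The first is "Patients within 52 weeks into this study: When adalimumab treatment is discontinued". After week 52 it is only the start of another biologic. Under Protocol 9.3, SAEs are reported "until the end of the PMOS (week 104 or discontinuation of this study". Protocol 12.0 applies the same end point to all AEs.

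**Which events count.** SAP 10.1 defines one AE follow-up period for every patient: "It should be between the date of initial Humira treatment and the date of initial Humira treatment + 755 days". It is not shortened when a patient leaves the study. SAP 10.2 places events outside this period outside the safety analysis. SAP 12 assigns events by onset date to days 0-167, 168-363 and 364-755. A fourth category holds any event in the follow-up period that occurs after Humira has ended.

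**The tables.** Table 5.2.1 lists these four as the "Categories for time of onset of ADRs", and Table 5.2.2 covers serious ADRs by time of onset. Both take the safety analysis set as their object and ask for the number analysed and for numbers and percentages by onset time. Neither asks for the number still under observation or for person-time. Tables 5.3.1 and 5.3.2 give numbers of events during and after treatment; after treatment means "Events that occurred after the date of final Humira treatment".

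**The concern.** A percentage for a time window has a clear meaning only if the patients in its denominator could have had an event recorded in that window. A patient who stops adalimumab at week 20 leaves the protocol's AE collection then. If that patient still counts in the week 24-52 and week 52-108 denominators, lack of observation is presented as absence of events.

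The post-treatment category is harder still to interpret. Patients still on treatment cannot have a post-treatment event, and those who stopped before week 52 leave systematic collection when they stop.

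SAP 3.1 says the results serve reporting to authorities and the reexamination application. A reader of Tables 5.2.1 and 5.2.2 could not separate a change in risk from a change in how many patients are being watched.

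**Working it through.** **1. The plan's own sample size.** The reference rate is "42.7% (61/143 patients" (Protocol 13.1). SAP 4.3 gives the alternative: "the expected observation was 55% and the estimated difference was 12.3% for the literature data 42.7". The one-sample formula is

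n = [z(0.975)·√(p0(1−p0)) + z(0.90)·√(p1(1−p1))]² / (p1−p0)²

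With p0 = 0.427 and p1 = 0.55, n = [1.960 × 0.4946 + 1.2816 × 0.4975]² / 0.123² = 170.7, so 171. This matches Protocol 13.1: "of 0.90 at an α level of 0.05 (two-tailed) would be 171 (one-sample test". Then 171 / (1 − 0.50) = 342, which the plan rounds to 350. The 350 and the 50% used below are therefore the plan's own figures. The 32% at week 24 comes from the all-case survey cited in the same section.

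**2. Patients under observation at the start of each window** (assuming all 350 are in the safety set).
- Week 24: 350 × (1 − 0.32) = 238
- Week 52: 350 × (1 − 0.50) = 175

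**3. Effect on a percentage.** Take ten patients with an ADR in a window.
- Weeks 24-52: 10/350 = 2.86%, against 10/238 = 4.20%. Ratio 238/350 = 0.68.
- Weeks 52-108: 10/350 = 2.86%, against 10/175 = 5.71%. Ratio 175/350 = 0.50.
- With 20% or 30% dropout at week 52 (assumption), 280 or 245 remain. Ten patients are then 3.57% or 4.08% of those at risk, and the ratio is 0.80 or 0.70.

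**4. Observed person-time as a share of whole-set person-time.** With exponential loss inside a window, the share is (S0 − S1)/ln(S0/S1), where S0 and S1 are the proportions observed at its start and end.
- Weeks 24-52: (0.68 − 0.50)/ln(0.68/0.50) = 0.585
- Weeks 52-104: 0.50 if everyone present at week 52 stays; (0.50 − 0.25)/ln 2 = 0.361 if half of them stay (assumption)
- Against the SAP's 56-week window, multiply by 52/56: 0.464 and 0.335

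**5. Comparison across windows.** Days 0-167, 168-363 and 364-755 make windows of 168, 196 and 392 days. Assume a constant 10 ADRs per 100 patient-years, with losses spread evenly within the first two windows and none after week 52. The whole-set percentage is the average share observed × [1 − exp(−0.10 × days/365.25)].
- Weeks 0-24: 0.84 × 4.50% = 3.8%
- Weeks 24-52: 0.59 × 5.22% = 3.1%
- Weeks 52-108: 0.50 × 10.18% = 5.1%

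The underlying rate is constant, yet the displayed values go down and then up. If half of the week-52 patients leave evenly over the last window (assumption), its share is 0.375 and its value 3.8%, level with the first.

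**6. End of collection.** Days 0 to 755 are 756 days, or 108 weeks. Protocol collection ends at week 104 at the latest, so the last 28 days of the third window lie beyond it even for completers.

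**The case against.** Several objections have weight.

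- *The per-window denominator is inferred.* No sentence in the SAP says that each window's percentage is divided by the whole safety set. This stands. The inference rests on the stated analysis object and the absence of any other number. If something else was meant, it needs to be written down.
- *Late events can still enter.* SAP 10.2 builds the AE data by matching CRF data with safety information data. A reader might infer that early stoppers cannot contribute later events at all. The documents support only that they are no longer under systematic protocol collection. Patients who stop after week 52 stay under observation until another biologic starts, so the post-treatment category has a real observed population.
- *Retention appears elsewhere.* Table 3.1 groups time to treatment completion at 168, 364 and 728 days, and Table 1.3.1 counts fixed CRFs. A reader could approximate the numbers, but only by combining tables. The person-time rates in Table 5.2.4 and the continuation curves in Tables 5.8.1 and 5.8.2 are limited to the literature analysis. Table 5.2.4 also covers only serious ADRs during treatment, by baseline MTX dose.
- *The 50% is a planning allowance.* This is true; actual retention will set the actual factor.

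A reader might also conclude that early stoppers' AE follow-up should be cut off in SAP 10.1 at treatment stop. That would do harm: under SAP 10.2, events outside follow-up leave the safety analysis, so genuine post-treatment ADRs would be lost.

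**Conclusion.** The point holds for Tables 5.2.1 and 5.2.2. On the natural reading, their later-window percentages are about 0.68 and 0.50 of the percentages among patients at risk at the plan's dropout allowance. The last factor is 0.70 to 0.80 if week-52 dropout is 20% to 30%. These figures assume a safety set of 350 and a whole-set denominator. The post-treatment percentage has no clear meaning on the whole set. The primary endpoint is not affected.

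Two stronger readings are not supported. A reader might expect the tables to show ADR risk falling steadily with time on drug. Because the windows are unequal, a constant rate gives about 3.8%, 3.1% and 5.1%, so the percentages are simply not comparable in either direction. A reader might also extend the percentage problem to Tables 5.3.1 and 5.3.2. Those ask for counts only. The risk there is that a small post-treatment count looks reassuring when the number of patients observed after stopping is not shown.

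**What to change.** - Keep the day +755 rule in SAP 10.1 for including events, so that no post-treatment ADR is dropped.
- In Tables 5.2.1 and 5.2.2, show for each calendar window the number of patients under protocol observation at its start. Use that number as the denominator for events with onset under observation.
- Add events per 100 patient-years of observation for each window. Start-of-window denominators alone correct neither for unequal window length nor for losses within a window.
- List separately any event with onset after the patient's protocol observation ended.
- For the post-treatment category, use the patients observed after stopping as the denominator. State that this category overlaps the three calendar windows.
- In Tables 5.3.1 and 5.3.2, add the number of discontinued patients observed after stopping.
- Reconcile the protocol's end of AE collection (week 104 or study discontinuation) with the SAP's day +755 (week 108).

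The cost is SAP wording and programming, with no new data. SAP 10.1 already derives the dates of final treatment and survey discontinuation, and the planned ends of the first and second CRFs (+167 and +363 days) coincide with the first two window boundaries. There is also a precedent: Table 3.2.2 already restricts its denominator to patients with fixed week-104 CRFs.

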7.0 Study Objective (s)

In daily clinical setting, patients with RA who receive adalimumab (Humira[®]) and high-dose MTX (≥ 12 mg/week) will be observed prospectively and the effectiveness will be assessed by DAS28 and mTSS. In addition the safety of the combination of adalimumab and high dose MTX will be assessed in terms of the incidence and pattern of the occurrence of adverse events.

The primary objective of the study is to assess the clinical effectiveness of adalimumab in combination with high dose MTX (≥ 12 mg/week). This will be measured by assessing the percentage of patients with the DAS28 score of < 2.6 at week 52.

The secondary objective of the study is to assess the clinical effectiveness of adalimumab in combination with high dose MTX (≥ 12 mg/week) by assessing the proportion of patients with a change in the following variables from baseline to week 104:

- Clinical Disease Activity Index (CDAI)
-

- Simplified Disease Activity Index (SDAI)
- The severity of functional impairment (HAQ)
- The health-related quality of life (EQ-5D)
- The inhibition of structural progression will be assessed by measuring the modified Van der Heijde Total Sharp Score (mTSS).

The safety profile will be assessed by measuring the following variables:

- All serious adverse events (SAEs) and adverse events (AEs)

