9.2 Relationship to Pharmaceutical Product

If an adverse event is occurred in the observation period, the physician will assess the causality of adalimumab with reference to the latest package inserts of adalimumab and concomitant drugs (e.g., methotrexate, corticosteroids). When the causality of an adverse event to the use of a concomitant drug other than adalimumab is suspected, the physician will describe the suspected drug.

The physician will use the following definitions for any adverse event being collected as an endpoint/data point the study and for all serious adverse events, to assess the relationship of the adverse event to the use of the pharmaceutical product:

Probable: An adverse event has a strong temporal relationship to the study drug or recurs on re-challenge, and another etiology is unlikely or significantly less likely.

Possible: An adverse event has a strong temporal relationship to the study drug, and an alternative etiology is equally or less likely compared to the potential relationship to study drug.

Not related: An adverse event is due to an underlying or concurrent illness or effect of another drug is not related to the study drug (e.g., has no temporal relationship to study drug or has a much more likely alternative etiology).

Impossible to judge:

If an investigator's opinion of "not related" to pharmaceutical product is given, **an alternate etiology must be provided by the investigator.**

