2.00	2/15/2016		Changes in overall description methods Review of figures/tables and definitions in association in response to periodic safety report
3.00	3/15/2016		Review of figures/tables and definitions in response to reexamination
4.00	7/22/2016		Addition of figures/tables and definitions in response to periodic safety report
5.00	9/15/2017		Addition of figures/tables and definitions for the final analysis
6.00	4/9/2018		Addition of tables as adjustments prior to the implementation of the final analysis

2. Definition of terms and abbreviations

The terms and abbreviations used in this statistical analysis plan are defined as follows.

Terms and abbreviations	Definitions
Adverse event	An adverse event (AE) refers to any unfavorable and unintended sign (including an abnormal laboratory finding), symptom or disease occurred in patients, whether or not considered related to the drug used.
Adverse reaction	Adverse events for which a causal relationship with Humira cannot be ruled out were handled as adverse reactions (ADRs).
Summary statistics	Summary statistics include the number of patients, mean, standard deviation, minimum, median, maximum.
MedDRA/J	Medical Dictionary for Regulatory Activities / Japanese edition
SOC	MedDRA/J System Organ Class
PT	MedDRA/J Preferred Term
LLT	MedDRA/J Lower Level Term
ACR	American College of Rheumatology
CDAI	Clinical Disease Activity Index

Terms and abbreviations	Definitions
CRP	C-Reactive Protein
DMARDs	Disease Modifying Antirheumatic Drugs
DAS	Disease Activity Score
EQ-5D	EuroQol Questionnaire 5 Dimensions
EULAR	European League Against Rheumatism
ESR	Erythrocyte Sedimentation Rate
HAQ	Health Assessment Questionnaire
TSS	Total Sharp Score
mTSS	modified Total Sharp Score
MTX	Methotrexate
RA	Rheumatoid Arthritis
SDAI	Simplified Disease Activity Index
VAS	Visual Analog Scale
Children	Patients aged < 15 years
Adults	Patients aged between ≥ 15 years and < 65 years
Elderly	Patients aged ≥ 65 years

3. Purpose and rules of this statistical analysis plan

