10.2. Safety analysis

Name of data	Derivation and calculation methods
Adverse event	For adverse event-related data, “an AE matching list”, the data set through the matching activities (matching of CRF data and safety information data), should be used. AEs with the same patient number should be aggravated and counted as one event when the PT is the same. However, when the novelty (known/unknown) is different within the same PT, such as in Appended Form 2, they should be tabulated separately.
Seriousness of AE	For seriousness of an AE aggravated from a single patient as the same PT, seriousness set through AE matching activities should be set in the following order of priority. Serious Non-serious
Causal relationship of AE	Where the causal relationship set through AE matching is other than “not related”, the causal relationship is defined as related. For causal relationship of an AE aggravated from a single patient as the same PT, causal relationship set through AE matching activities should be set in the following order of priority. Related Not related
Outcome of AE	Outcomes of AEs aggravated from a single patient as the same PT should be set in the following order of priority. Fatal Unknown Not recovered/Not resolved Recovered/Resolved with sequelae Recovering/Resolving Recovered/Resolved
Adverse reaction	AEs of which causal relationship is other than “not related” set through the AE matching activities are defined as ADRs.
Serious AEs	AEs of which seriousness set through the AE matching activities is “serious” are defined as serious AEs.
AEs outside the follow-up period	These should be handled as outside the safety analysis. AEs are defined that occurred prior to the start date of Humira treatment or at week 108 (treatment start date + 755).

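### Every SAP safety table split by MTX dose counts only Humira-related reactions, so events attributed to MTX instead of Humira are missing from the dose comparison

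*SAP*

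**What the plan says.** Protocol section 7.0 sets the safety objective for the drug pair: "the safety of the combination of adalimumab and high dose MTX will be assessed", with all SAEs and AEs as the variables.

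Three SAP outputs relate safety to MTX dose. Tables 5.2.3 and 5.2.4 (section 13.2) show the "number and percentage of SOC and PT by category of MTX dose at the start of treatment regarding serious ADRs"; Table 5.4.4-style breakdowns do not exist, and Table 5.2.4 is the version per 100 patient-years during Humira treatment. Table 5.4 gives ADR incidence by the background factors of SAP section 11, which include the concomitant MTX dose at the start of Humira.

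The SAP's definitions section states: "Adverse events for which a causal relationship with Humira cannot be ruled out were handled as adverse reactions (ADRs". SAP 10.2 makes this operational: "AEs of which causal relationship is other than “not related” set through the AE matching activities are defined as ADRs".

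Under Protocol 9.2, "the physician will assess the causality of adalimumab with reference to the latest package inserts of adalimumab and concomitant drugs". Its definition of *Not related* reads: "An adverse event is due to an underlying or concurrent illness or effect of another drug is not related to the study drug". *Possible* covers a strong temporal relationship where "an alternative etiology is equally or less likely compared to the potential relationship to study drug". *Impossible to judge* is a separate category. Where a concomitant drug is suspected, "the physician will describe the suspected drug".

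**The concern.** The columns of these tables are defined by the dose of one drug, while the events in them are filtered by causality to the other. The filter is therefore not neutral for the comparison shown: it removes the events that a physician puts down to MTX and not to Humira. The protocol introduction cites retrospective data in which the ADR profile did not differ significantly between lower and higher MTX doses, and uses this to argue for prospective study. If the prospective tables count only Humira ADRs, they carry the same blind spot, and a flat pattern across bands could be read as reassurance about MTX dose that the count cannot give. Tables 5.2.3 and 5.2.4 are produced for the literature analysis, so this is the form in which readers outside the sponsor would see the dose comparison.

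**Working it through.** The plan gives no figure on this point, so there is none to reproduce. The check is a trace of definitions, followed by arithmetic on assumed risks.

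**Trace**

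1. Tables 5.2.3, 5.2.4 and 5.4 count ADRs (SAP 13.2).
2. An ADR is any AE whose final causality to Humira is something other than *Not related* (SAP 2 and 10.2).
3. *Not related* includes an event due to another drug (Protocol 9.2).
4. So an event attributed to MTX and finally classed *Not related* to Humira is not an ADR and is in none of the three tables.
5. Events rated *Probable*, *Possible* or *Impossible to judge* are ADRs and remain, even if MTX is also suspected. When the same preferred term recurs in one patient, SAP 10.2 gives priority to the related classification, so that event remains as well.
6. Does another summary table fill the gap? Tables 5.1.1, 5.3.1 and 5.3.2 count AEs or serious AEs whatever the cause, but split them by seriousness or by treatment status and timing, not by MTX dose. No table description uses the suspected concomitant drug.

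**When the loss distorts the comparison**

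Let R be the true ratio of event risk, highest to lowest band, and let k be the share of events kept in each band. Then

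displayed ratio = R × k(high) / k(low).

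The ratio is understated only if k(high) < k(low), that is, if the share lost rises with dose.

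*Assumed risks (not in the documents):* 6% in the 12 to <14 mg/week band and 10% in the ≥16 mg/week band, so R = 10/6 = 1.67. All events in the low band are kept.

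| Part of the 4-point excess attributed to MTX alone | Displayed risks | Displayed ratio |
|---|---|---|
| 0% | 10% v 6% | 1.67 |
| 50% | 8% v 6% | 1.33 |
| 100% | 6% v 6% | 1.00 |

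If instead half of the events are lost in both bands, the display is 5% v 3%, ratio 1.67, with no distortion.

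*A second set of assumptions:* Humira-related serious ADRs are equal in all bands, and MTX-only serious events rise across the three bands by 0.5/1/2% or by 1/3/5%. The all-cause ratio, top to bottom band, is:

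| Humira-related risk | MTX-only 0.5/1/2% | MTX-only 1/3/5% |
|---|---|---|
| 3% | 5/3.5 = 1.43 | 8/4 = 2.00 |
| 5% | 7/5.5 = 1.27 | 10/6 = 1.67 |
| 8% | 10/8.5 = 1.18 | 13/9 = 1.44 |

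The ADR-only table would show 1.00 in all six cells. With no MTX-only events, both counts give 1.00.

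**The case against.** The strongest reply is that this is a survey on Humira under the post-marketing ordinance, so Humira ADRs are its natural unit, and the same unit keeps comparability with the earlier data by MTX dose. All patients must start on at least the qualifying MTX dose, so the all-cause tables 5.1.1 and 5.3.2 already describe the safety of the combination. No objective calls for a comparison across MTX bands, and Tables 5.2.3 and 5.2.4 are literature-analysis outputs with no test specified. This stands as a reason to keep the ADR columns and to treat the gap as one missing stratification. It does not supply that stratification.

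Four stronger readings are tempting and are not supported:

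- *Any event with MTX suspected is lost.* A reader might infer this, but both drugs can be suspected, and *Possible* and *Impossible to judge* events are kept. The final causality is also set through the AE matching, whose rule for changing a physician's rating is not given.
- *The tables were designed to show MTX toxicity.* The SAP does not say so. That use is inferred from the titles, the bands and the combination objective.
- *The comparison is biased toward no difference.* This holds only if the share lost rises with MTX dose. An equal share leaves the ratio unchanged.
- *All-cause counts should replace ADRs as the main count.* Background events dilute a gradient too: adding an assumed 6% to each of 6% and 10% gives 16/12 = 1.33 in place of 1.67. Each count is imperfect in a different way.

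**Conclusion.** The gap is real but limited. No planned summary table shows all-cause events by MTX dose, and those split by dose leave out events finally attributed to MTX and judged not related to Humira. That these events are excluded follows from the definitions alone. How many there are, and whether they distort the comparison, cannot be derived: the documents give no event rates, no attribution pattern and no matching rule. Under the assumptions shown, a true ratio of 1.67 could be displayed as anything from 1.67 to 1.00. The primary effectiveness endpoint is not affected. This is a cheap improvement to a secondary tabulation that bears on the combination-safety objective.

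**What to change.** - In Tables 5.2.3 and 5.2.4, add a column of all serious AEs regardless of causality, by baseline MTX band: the count in 5.2.3 and the rate per 100 patient-years in 5.2.4.
- For the MTX-dose row of Table 5.4, add all AEs regardless of causality.
- Keep the Humira-ADR columns unchanged.
- State in the SAP that any conclusion on safety by MTX dose is read from both columns, not from ADRs alone.
- Add a count of events with MTX recorded as a suspected drug only if that item can be retrieved from the AE data. Protocol 9.2 asks the physician to describe the drug but does not say on which form, and the AE items in SAP 10.2 do not list it.

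Cost: SAP wording and a few columns. The all-cause columns need no new data, because Protocol section 12.0 has every AE documented on the CRF. The downsides are higher displayed event rates and some dilution of the all-cause column by background events. The comparison across bands remains observational in either column.
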